**22 Consent and Translation**

*Click on the check box (or double click and type an "X" if using Google Docs) to indicate that consent will be translated.*

**The study population will likely include participants whose limited English speaking status requires translation of the consent form.**

**Translation Process**

*Click on the check box (or double click and type an "X" if using Google Docs) that best describes the translation process, either 21 or 22.*

**23  The consent documents will be translated by a certified translator.**

**24  A non-certified translator will translate the consent documents.**

*If selected, complete the next two questions below.*

**i  Describe the translator's qualifications**

*To input text, click in the light grey area below.*

**ii  Another individual will confirm that the translation is accurate and appropriate.**

**Waiver of Documentation of Informed Consent**

*To approve a waiver of documentation of informed consent, one of the following options below must be justified by the researcher.*

***Only complete the sections below if requesting a waiver of documentation of informed consent. If not requesting a waiver of documentation of consent, skip to 27.***

*Please choose one waiver option and provide additional information as prompted. The Office of Research Support and Compliance recommends using Waiver Option 2 in most cases.*

**25**

## **Waiver Option 1**

*Provide confirmation for the following criteria and follow the additional instructions.*

***Additional Instructions:***

- 1. Include this choice in the informed consent form.*
- 2. Articulate the destruction process for signed consent forms in the privacy and confidentiality section.*

*Click on the check box (or double click and type an "X" if using Google Docs).*

- a  The only record linking the subject and the research would be the consent document.**
- b  The principal risk would be potential harm resulting from a breach of confidentiality.**
- c  Each subject will be asked whether the subject wants documentation linking the subject with the research, and the subject's wishes will govern.**

**26**

## **Waiver Option 2**

*Provide confirmation for the following criteria and follow the additional instructions.*

*Click on the check box (or double click and type an "X" if using Google Docs).*

- a  The study is minimal risk.**
- b  Written consent would not be required outside the research context.**

**27**

## **Waiver Option 3**

*Provide confirmation for the following criteria and provide additional information as requested.*

*Click on the check box (or double click and type an "X" if using Google Docs).*

**a  The subjects or legally authorized representatives are members of a distinct cultural group or community in which signing forms is not the norm**

**b  Describe the cultural group or community.**

*To input text, click in the light grey area below*

**c  The research presents no more than minimal risk of harm to subjects.**

**d  There is an appropriate alternative mechanism for documenting that informed consent was obtained.**

**e  Describe mechanism for documenting that informed consent was obtained**

*To input text, click in the light grey area below*

## **Waiver or Alteration of Informed Consent**

*To approve a waiver or alteration of informed consent all of the following criteria below must be justified by the researcher.*

*Only complete the sections below if requesting a waiver of informed consent. If not requesting a waiver or alteration of consent, skip to 31.*

**28 The research involves no more than minimal risk to the subjects.**

*To input text, click in the light grey area below*

**29 The waiver or alteration will not adversely affect the rights and welfare of the subjects.**

[figure not shown]
*To input text, click in the light grey area below*

**30 The research could not practically be carried out without the waiver or alteration (it is impracticable to perform the research if obtaining informed consent is required and not just impracticable to obtain consent).**

*To input text, click in the light grey area below*

**31 If the research involves using identifiable private information or identifiable biospecimens, the research could not practicably be carried out without using such information or biospecimens in an identifiable format.**

*To input text, click in the light grey area below.*

## Deception and Debriefing

**Only complete the sections below if requesting an alteration of informed consent that involves deceiving research participants.** If this study does not involve deception, skip to 35.

See IRB Policies and Procedures Section 15 for a description of deception.

Click on the check box (or double click and type an "X" if using Google Docs).

**32**  **It is appropriate to provide additional pertinent information to the subject after research activities are complete (e.g., the researcher needed to deceive the subject to the nature of the study).**

**33**  **Research participants will have the opportunity to withdraw their data during the debriefing.**

**34 Describe the nature of deception and why it is necessary to conduct the research.**

*To input text, click in the light grey area below.*

**35 Describe debriefing procedures.**

*To input text, click in the light grey area below.*

Participants will be given additional information about the purpose of the study and information about treatment for social anxiety. Participants that are not eligible for or opt-out of the intervention will be debriefed immediately after completing part 1 of the study. If participants complete the intervention component they will be debriefed following the final assessment (week 2 follow-up)

## BENEFITS

**36 Benefits to Society**

*Describe the scientific and societal benefit(s) below.*

*To input text, click in the light grey area below.*

Findings will contribute to the understanding of the impact of teleconferencing specifically on social anxiety. This may be useful in designing effective intervention efforts to reduce social anxiety around teleconferencing.

## Benefits to Participants

*Click on the applicable check box (or double click and type an "X" if using Google Docs).*

**37**  **There is no anticipated direct benefit to participants.**

**38**  **There are anticipated benefits to participants.**

**39** **If applicable, describe the potential direct benefits to participants.**

*To input text, click in the light grey area below.*

## RISKS

**40** **Describe the risks associated with each activity in this research**

*To input text, click in the light grey area below.*

The research includes some risk of emotional discomfort.

**41** **Describe how each risk is mitigated/minimized.**

*To input text, click in the light grey area below.*

The emotional discomfort will be related to perceived social interactions and is transient. Participants will be able to stop the study at any point (simply by closing their browser window). At any point during the study participants will be able to reach out to the researchers to discuss any emotional discomfort should it be persistent. At the end of the study participants will be debriefed and learn that the interaction was not live, which should mitigate any further discomfort. Furthermore, participants will be provided with referral resources at the end of the study.

## Data Safety Monitoring

*For additional information regarding data safety monitoring boards and data safety monitoring plans, please see Section 21 of our [Policies and Procedures](#).*

*Click on the check box (or double click and type an "X" if using Google Docs).*

**42**  **This study is minimal risk and does not require a Data Safety Monitoring Plan (DSMP) or a Data Safety Monitoring Board (DMSB).**

**43**  **This study does not have a Data Safety Monitoring Board, but researchers have an internal plan/policy to monitor for safety.**  
*Complete Data Safety Monitoring Details (44-51).*

**44**  **This study has a Data Safety Monitoring Board (DSMB).**  
*Complete Data Safety Monitoring Details (44-51) or upload this study's Data Safety Monitoring Board's charter.*

## **Data Safety Monitoring (Details)**

**45** **How is safety information collected?**  
*To input text, click in the light grey area below.*

**46** **When will safety data collection start (for each participant or for the whole study, as applicable)?**  
*To input text, click in the light grey area below.*

**47** **How frequently will safety data be collected?**  
*To input text, click in the light grey area below.*

**48** **Who will review the data for safety?**  
*To input text, click in the light grey area below.*

**49** **How frequently will data be monitored for safety concerns?**  
*To input text, click in the light grey area below.*

**50** **What data will be reviewed?**

*To input text, click in the light grey area below.*

**51** **State the frequency or periodicity of the review of cumulative data?**

*To input text, click in the light grey area below.*

**52** **State any conditions that would trigger an immediate suspension of the research.**

*To input text, click in the light grey area below.*

### **Early Withdrawal**

***Only complete this section if there are planned conditions under which a participant will be withdrawn from the study. If not applicable, skip to 56.***

*Include this information in your consent form.*

**53** **List the criteria for withdrawing individual participants from the study (e.g., safety or toxicity concerns, emotional distress, inability to comply with the protocol, or requirements from study sponsor).**

*To input text, click in the light grey area below.*

**54** **Describe any necessary procedures for ensuring the safety of a participant who has withdrawn early.**

*To input text, click in the light grey area below.*

**55** **Describe any pre-specified criteria for stopping or changing the study protocol due to safety concerns.**

*To input text, click in the light grey area below.*

## REQUIRED DISCLOSURES

### Required Consent Disclosures

*Identify each element below that may require additional information to be disclosed in the consent form.*

*Click on the check box (or double click and type an "X" if using Google Docs).*

56  **It is reasonable that researchers could discover or suspect child or elder abuse.**

57  **It is reasonable that researchers could learn of an incident that could require reporting under Title IX.**

58  **It is reasonable that researchers could discover incidental findings or other information of medical interest about a participant's previously unknown condition.**

59 **Articulate methods for addressing and reporting incidental findings, if applicable.**  
*To input text, click in the light grey area below.*

## PRIVACY AND CONFIDENTIALITY

### 60 Privacy

*Describe how you will protect the identity and privacy of study participants during each phase of research. Privacy focuses on the individual participants rather than data. In this section, researchers should focus on issues such as where research activities take place and how participant involvement is protected from non-participants.*

*Describe methods to ensure participants' privacy during identification, recruitment, screening, the consent process, the conduct of the study, and dissemination of data.*

*To input text, click in the light grey area below.*

All data associated with the project will be kept strictly confidential. Except for the questionnaires that are completed during participant screening, all data will be de-identified with a generated ID number. Audio data will be accessed only by researchers directly involved in the project. To further protect subjects' privacy, all data will be paperless with all data being encrypted and stored securely on Qualtrics, Gorilla, and UT Box. Only members of the research team will have access to the project's data. Publications resulting from the research will not include any personally identifiable information

## **Confidentiality and Data Security Plan**

*Click on the check box (or double click and type an "X" if using Google Docs) that best describes the confidentiality and data security plan and provide additional details regarding how you will protect the confidentiality of data or address confidentiality concerns.*

We will use Qualtrics/Gorilla - generated user IDs to protect confidentiality. All potential identifying information will be stored separately and securely on UT Box. All non-identifiable data will be stored in HIPAA secure, encrypted digital files in Qualtrics, Gorilla, and UT Box. Non-identifiable data will be saved indefinitely, whereas files containing identifiable data will be deleted on the date of project completion. Identifiable and non-identifiable information will be stored separately to further protect confidentiality.

**61**  **Identifiers will be coded to protect confidentiality.**

**61a** **If true, state how data is coded and where identifiers are stored.**

*To input text, click in the light grey area below.*

Data will be coded using a random number generator in Qualtrics and stored internally within Qualtrics as well as in a single spreadsheet stored separately from the data on UT Box.

**62**  **Identifiable data will be destroyed.**

**62a** **If true, describe destruction plan and timeline**

*To input text, click in the light grey area below.*

The document linking identifiers and data will be destroyed at the end of the study. The audio data will only be destroyed following the completion of analyses.

**63**  **Identifiable data will not be destroyed.**

**63a** **If true, provide rationale for retaining identifiable data indefinitely.**

*To input text, click in the light grey area below.*

## 64 Data Access

Click on the check box (or double click and type an "X" if using Google Docs) for each group of individuals that will have access to study data.

If you plan on creating a repository, complete the repository form as well.

|  |   |   |
|--|---|---|
|  Study Team Members |  External Collaborators                           |  Data coordinating center |
|  Sponsor            |  Future Sharing with other researchers |   |
|  Others                        |   |   |

Describe below. To input text, click in the light grey area below.

## 65 Describe data sharing plan for each group checked above and state whether researchers plan on sharing identifiable, coded, or de-identified data

To input text, click in the light grey area below.

Study team members and Sponsor will have direct access to UT Box and Qualtrics. Shared data will only include de-identified data.

## Certificate of Confidentiality

Click on the check box (or double click and type an "X" if using Google Docs) to identify each element below that may require additional information to be disclosed in the consent form.

If a Certificate of Confidentiality is not applicable for this study, skip to 68.

- 66  The study requires a Certificate of Confidentiality.
- 67  NIH has issued a Certificate of Confidentiality for this study.
- 68  A Certificate of Confidentiality has not been obtained, but there are plans to apply for one.

## COMPENSATION AND COSTS

### Compensation

*Click on the check box (or double click and type an "X" if using Google Docs).*

**69**  **Subjects receive compensation.**

**70**  **Subject will not receive compensation.**

*Skip to question 74 if subjects will not receive compensation.*

### 71 Total Amount of Compensation

*To input text, click in the light grey area below.*

Participants will receive course credit proportional with the time spent engaged in study activities (up to 5 credits) if participating through the undergraduate subject pool.

Participants will be entered into a drawing for each part of the study they complete, participants can receive up to \$85 if they are drawn for all three parts.

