**\*All activities will be conducted online via Qualtrics and Gorilla.**

**Recruitment and Eligibility.** Participants ( $N=2,000$ ) will be recruited via a range of online recruitment methods including the research pool, social media, and email. We will recruit both male and female participants regardless of race or ethnicity. Potential participants will complete the study in two stages, all online.

**Stage 1 Procedures:** Participants will complete a series of questionnaires. Participants will be randomized to one of two groups if they are eligible for the second stage of the study.

**Positive Interaction.** Participants in this condition will be prompted with a question by audience members who were positive in their interactions with the other audience members.

**Negative Interaction.** Participants in this condition will be prompted with a question by audience members who were negative in their interactions with the other audience members.

At the end of this stage of the study participants will be able to choose whether they would like to continue to the intervention.

**Stage 2 (Intervention) Procedures.** Participants may be asked to wait 1-week prior to beginning the intervention. Participants will complete four intervention (i.e. exposure) sessions within two weeks. Participants will sign up for all four sessions at the start of the intervention.

For the first session:

- 1) Participants will receive a brief standardized psychoeducation module, presented via a video recording. This video will explain the intervention, its rationale, and the procedure.

For each subsequent session:

- 2) Participants will then complete up to 10 analogue teleconferencing calls, each lasting a maximum of two minutes. During each call participants will be prompted by one of the audience members.
- 3) Between speeches participants will have a 1-minute break.
- 4) Participants will complete the subjective units of distress scale (SUDS) before and after each speech trial.

**Attention Guidance Condition.** The experimental attention guidance condition consists of three unique components: (1) the intervention rationale will include information about the importance of visually attending to the faces of the audience; (2) participants will be given target audience members to focus their gaze on during their impromptu response. They will be told that they should look at and focus on the target audience member for the whole response.

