### 73 Proration Schedule

*To input text, click in the light grey area below.*

Participants that are participating for course credit will receive .25 credits for every 15 minutes of participation in the study.

Participants not participating for credit will be entered into a different drawing for each part of the study they complete. The drawing for part 1 of the study will be for \$10. The drawing for part 2 of the study will be \$50. There will be 5 drawings for each part. Participants can receive up to \$60 that will be provided digitally through Venmo or Paypal.

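### Do the two different maximum drawing payments ($85 over three parts, $60 over two) call for a change to the plan?

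*Protocol*

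**What the plan says.** Two adjacent fields of the Protocol describe the cash drawings.

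- Section 71 (Total Amount of Compensation) first gives course credit to people recruited through the undergraduate pool. A separate paragraph then says "Participants will be entered into a drawing for each part of the study they complete" and that "participants can receive up to \$85 if they are drawn for all three parts".
- Section 73 (Proration Schedule) sets out the detail. On entry: "Participants not participating for credit will be entered into a different drawing for each part of the study they complete". On prizes: "The drawing for part 1 of the study will be for \$10. The drawing for part 2 of the study will be \$50". On number: "There will be 5 drawings for each part". On the ceiling: "Participants can receive up to \$60 that will be provided digitally through Venmo or Paypal".

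The rest of the Protocol works with two parts. Section 11 says "Potential participants will complete the study in two stages, all online", the inclusion and exclusion criteria in section 13 are set for Part 1 and Part 2, and section 21 describes one consent document for each. Table 1 in section 11 gives the 1-week and 2-week follow-ups their own columns but calls neither of them a part.

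**The concern.** The two fields cannot both be right about the ceiling or about how many parts carry a drawing. Read literally, they also differ on who is entered: section 71 speaks of participants in general, section 73 only of those not taking credit. Since section 19 says recruitment is mainly through the university research pool, the entry rule would affect the larger source of participants.

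At stake would be the accuracy of a term offered to participants, and the ability of staff to run the drawings by one rule. A further question is what finishing part 2 means for the larger prize, because Table 1 separates the follow-ups from the intervention. If the missing third part were the follow-ups, a reader might also wonder whether an incentive for completing them had been dropped.

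**Working it through.** **Inputs.** Section 71: maximum $85, three parts. Section 73: $10 for part 1, $50 for part 2, five drawings per part, maximum $60.

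**Step 1: reproduce section 73's figure.** Maximum = part 1 prize + part 2 prize = 10 + 50 = $60. This agrees with the stated $60, taking one win per part.

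**Step 2: try to reproduce section 71's figure.** 85 − (10 + 50) = $25 is left over. Allowing several wins per part does not help. With *a* wins of $10 and *b* wins of $50, each from 0 to 5, the total 10*a* + 50*b* is always a multiple of 10, so it can never equal 85. Winning all ten drawings would give 5 × 10 + 5 × 50 = $300.

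**Step 3: look for another source of the $25.**
- Course credit is counted in credits, not dollars, and section 71 states it separately.
- The follow-ups could be a third part, but nothing calls them one or attaches a prize to them. Section 35 says "If participants complete the intervention component they will be debriefed following the final assessment (week 2 follow-up"); that fixes the time of debriefing and says nothing about payment.
- Both fields are complete, with no redaction or amendment log involved.

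The $25 and the third part therefore remain unexplained.

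**Step 4: test the entry rule.** Section 71 is a summary field and section 73 the detailed schedule. Section 71 gives credit to pool participants and then describes the drawing; it does not say that credit participants also enter it. Section 73 can be read as completing that sentence: credit for one group, drawings for the other. The wording is loose, but the two rules are not incompatible.

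**Step 5: trace any route to the results.**
- Sample size: sections 14 and 15 give 2,000, justified by the need for enough people to enrol in and complete part 2. No payment figure enters.
- Outcome and model: the SAP names the Personal Report of Communication Apprehension as primary outcome and Bayesian multi-level models as the method. Payment is not a term in either.
- Comparison between groups: neither section 71 nor section 73 makes entry or prize depend on the interaction group or the exposure condition, so whichever figure applies, it applies alike to the groups compared.

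No estimate, interval or probability statement changes with the choice between $60 and $85.

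**The case for a change.** The strongest case for acting is that the conflict is certain, can be seen by reading two short fields, and faces participants. The maximum payment is part of what people are offered, one field promises $25 more than the other, and the repair costs a sentence. Staff running the drawings also need to know whether someone who finishes the four sessions but misses a follow-up qualifies for the $50.

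Much of this stands. The two fields do disagree on the ceiling and on the number of parts, and they should be made to agree. But what participants were actually told is in the consent documents, which section 21 says are attached and which are not in the text available here. If those carry a single figure, what remains is a stale sentence in a form. The completion rule for part 2 is missing detail, not a contradiction, and whoever runs the drawing can settle it when doing so. An estimate of extra prize money would need a third set of drawings that the documents never describe.

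**Conclusion.** The discrepancy is confirmed: $85 over three parts against $60 over two, with $25 and one part unaccounted for. It is a clerical slip, and no change to the plan follows. It touches no estimate, no error rate or power, no source of bias and no safety provision, and correcting it would not make the trial's conclusions any firmer. The apparent conflict over who enters the drawings is weaker, because the detailed schedule can be read as qualifying the summary.

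This conclusion rests on two things: that payment is the same across the groups compared, as both fields imply by making no distinction, and that the consent documents give participants one consistent figure, which cannot be checked here. If the second failed, the matter would be one of participant information for the ethics board and would still not bear on the statistical plan. The documents do not establish which figure was meant, and nothing in the analysis depends on knowing.
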